2.1.4 Safety endpoints

The safety analysis will be based on the reported adverse events, hypoglycemia, and other safety information, such as clinical laboratory data, and vital signs, etc.

Observation period

The observation period for safety data will be divided into 3 segments:

- The pre-treatment period is defined as the time between the date of signing of the informed consent (inclusive) and the first injection of IMP (exclusive),
- The on-treatment period is defined as the time from the first injection of IMP (inclusive) up to and including 3 days after the last injection of IMP (treatment-emergent AE [TEAE] period),
- The post-treatment period is defined as the time starting 4 days after last injection of IMP (after the TEAE period).

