2.1.4.2 Adverse events variables

Adverse event observation period

- The pre-treatment period is defined as the time between the date of signing of the informed consent and the first injection of IMP,
- The on-treatment period is defined as the time from the first injection of IMP up to and including 3 days after the last injection of IMP (treatment-emergent AE [TEAE] period),
- The post-treatment period is defined as the time starting 4 days after last injection of IMP (after the TEAE period).

All adverse events (including SAE, AESI) will be coded to a lower-level term (LLT), preferred term (PT), high-level term (HLT), high-level group term (HLGT), and associated primary system organ class (SOC) using the version of Medical Dictionary for Regulatory Activities (MedDRA) currently in effect at Sanofi at the time of database lock.

The occurrence of adverse events (including SAE and AESI) will be recorded from the time of signed informed consent until the end of the study or the resolution/stabilization of all SAE and AESI.

An adverse event of special interest (AESI) is an AE (serious or non-serious) of scientific and medical concern specific to the Sponsor’s product or program, for which ongoing monitoring and immediate notification by the Investigator to the Sponsor is required. Such events may require further investigation in order to characterize and understand them

AESI are listed below:

- ALT >3 x ULN;
- Serious allergic/hypersensitivity reactions;
- Pregnancy occurring in a female patient administered IMP/NIMP;
- Symptomatic overdose of IMP/NIMP

Table 3 - Criteria for AESI

AE Grouping	Criteria
AESI	
Serious allergic/hypersensitivity reactions	eCRF form “Hypersensitivity/Allergic”
Pregnancy	eCRF form “Pregnancy”
Symptomatic overdose	“Overdose of IMP” or “Overdose of NIMP” checked and “Symptomatic overdose” checked in eCRF form “Overdose”
ALT increase > 3X ULN	eCRF form “ALT increase”

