2.4.3.1 Extent of investigational medicinal product exposure

The extent of IMP exposure will be assessed by the duration of IMP exposure.

Duration of IMP exposure is defined as last dose date of IMP – first dose date of IMP + 1 day, regardless of unplanned intermittent discontinuations (see [Section 2.5.3](#) for calculation in case of missing or incomplete data).

Duration of IMP exposure will be summarized descriptively as a quantitative variable (number of patients exposed, mean, SD, median, minimum, and maximum). In addition, duration of treatment exposure will also be summarized categorically by numbers and percentages for each of the following categories and cumulatively according to these categories:

- 1 to 28 days,
- 29 to 56 days,
- 57 to 84 days,
- 85 to 126 days,
- 127 to 168 days
- 169 to 175 days
- 176 to 182 days
- >182 days

Additionally, the cumulative duration of treatment exposure will be provided, defined as the sum of the duration of treatment exposure for all patients, and will be expressed in patient years.

Number and percentages of patients by final dose at the end of the treatment will also be presented by each treatment group.

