2.4.5 Analyses of safety data

The summary of safety results will be presented by treatment group, for both the overall population and separately for each ethnic/race subgroup, for the 26-week randomized treatment period, unless specified otherwise.

All safety analyses will be performed on the safety population using the following common rules:

The “observation period” defined in [Section 2.1.4](#) is applicable in all safety analyses for the classification of AEs, determination of treatment-emergent Potentially Clinically Significant Abnormality (PCSA) values and the last on-treatment value for the laboratory, vital sign and ECG.

General common rules

All safety analyses will be performed on the safety population as defined in [Section 2.3.2](#), unless otherwise specified, using the following common rules:

- Safety data in patients who do not belong to the safety population (e.g., exposed but not randomized) will be listed separately
- The baseline value is defined as the last available value before the first dose of IMP
- PCSA values are defined as abnormal values considered medically important by the Sponsor according to predefined criteria/thresholds based on literature review and defined by the Sponsor for clinical laboratory tests, vital signs, and ECG. PCSA criteria will determine which patients had at least 1 PCSA during the treatment-emergent adverse event period, taking into account all evaluations performed during the treatment-emergent adverse event period, including nonscheduled or repeated evaluations. The number of all such patients will be the numerator for the treatment emergent PCSA percentage
- The treatment-emergent PCSA denominator by group for a given parameter will be based on the number of patients assessed for that given parameter in the treatment-emergent adverse event period by treatment group on the safety population.
- For laboratory parameters cited in the protocol as efficacy endpoints (including HbA1c and plasma glucose etc.), PCSA summaries will not be provided. These parameters will be summarized in [Section 2.4.4](#).

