2.4.5.1 Hypoglycemia

Analyses of hypoglycemia will be performed on the TEAE period as defined in [Section 2.1.4](#). Hypoglycemia will be classified as severe hypoglycemia, documented hypoglycemia (blood glucose ≤ 70 mg/dL and < 54 mg/dL), probable symptomatic hypoglycemia or pseudo hypoglycemia.

The number (%) of patients with at least 1 hypoglycemia, severe hypoglycemia and documented hypoglycemia (blood glucose ≤ 70 mg/dL and < 54 mg/dL), probable symptomatic hypoglycemia or pseudo hypoglycemia will be summarized respectively by treatment group during the TEAE period, as well as the incidence rate in patient years. Two types of incidence rates will be presented: the number of patients with at least 1 event per patient-year (calculated as the number of patients with at least 1 event / total exposure in patient-year), and the number of events per patient-year (calculated as the total number of events / total exposure in patient-years). Note: here exposure (in days) is the duration of TEAE period, i.e., duration of IMP treatment in days +1 (see [Section 2.1.4](#)).

A KM curve will also be provided by treatment group for the time to first severe hypoglycemia or documented hypoglycemia during the TEAE period for the entire 26-week treatment period only.

A listing of patients for all events reported on the dedicated e-CRF “Hypoglycemic event information” page will be provided with each category flagged (i.e., severe hypoglycemia, documented hypoglycemia, probable symptomatic hypoglycemia and pseudo hypoglycemia).

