When a patient has more than 1 measurement from the central laboratory for the same laboratory parameter on the same date, the average of the measurements will be used. For the same laboratory parameter, if a patient has more than 1 measurement on different dates for the same scheduled visit, the value closest to the date of the visit will be used for the scheduled visit. When the values for the same scheduled visit are equidistant, the last value should be used for the scheduled visit. Similar rules will be applicable to a patient who has more than 1 set of measurements for the same vital sign parameter (i.e., SBP, DBP, or HR) on the same date.

26-week randomized treatment period

The 26-week randomized treatment period is the time from first administration of IMP to the last administration of IMP on or before Visit 19/Week 26 (or Day 182 if Visit 19/Week 26 date is missing). This is for defining EOT status at Week 26 and analyzing selected efficacy parameters during the 26-week randomized core treatment period.

TEAE period for the 26-week randomized treatment period

The TEAE period for 26-week randomized treatment period is (1) the time from the first administration of the IMP up to 10 days (1 day for hypoglycemia) after the last administration of IMP if the patient discontinued treatment on or before Visit 19/Week 26 (or Day 182 if Visit 19/Week 26 date is missing), or (2) the time from the first administration of the IMP to the administration at Visit 19/Week 26 (or Day 182 if Visit 19/Week 26 date is missing) if the patient remained treated beyond Visit 19/Week 26. This is for the purpose of safety analyses during the 26-week randomized treatment period.

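### The SAP defines two different treatment-emergent windows for the same 26-week safety tables, and hypoglycemia rates count events on one window but divide by the length of another

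*SAP*

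**What the plan says.** SAP 2.1.4 defines the on-treatment period for safety data as running from the first injection "up to and including 3 days after the last injection of IMP (treatment-emergent AE [TEAE] period". Section 2.1.4.2 repeats this for adverse events and adds: "The post-treatment period is defined as the time starting 4 days after last injection of IMP (after the TEAE period". Section 2.4.5 says that the 2.1.4 observation period "is applicable in all safety analyses for the classification of AEs, determination of treatment-emergent Potentially Clinically Significant Abnormality (PCSA) values".

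Section 2.5.3 then gives a second definition, under a paragraph on the TEAE period for the 26-week randomized treatment period. For patients who stop on or before Visit 19/Week 26 it is "the time from the first administration of the IMP up to 10 days (1 day for hypoglycemia) after the last administration of IMP". For patients treated beyond Visit 19 it ends at the Visit 19 administration (Day 182 if that date is missing). The paragraph states that it serves the safety analyses of the 26-week period.

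For hypoglycemia, 2.4.5.1 says "Analyses of hypoglycemia will be performed on the TEAE period as defined in" Section 2.1.4. The event rate is "calculated as the total number of events / total exposure in patient-years", and a note adds that "exposure (in days) is the duration of TEAE period, i.e., duration of IMP treatment in days +1", again citing 2.1.4. Section 2.4.3.1 defines the duration of IMP exposure as the last dose date minus the "first dose date of IMP + 1 day, regardless of unplanned intermittent discontinuations".

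**The concern.** The two windows cannot be assigned to different outputs. Section 1.1 describes a single 26-week treatment period, 2.4.5 presents safety results for that period, and 2.4.5.2 generates the TEAE summaries in it. Two programmers working from this SAP could therefore produce different TEAE and hypoglycemia tables, and both could defend their output from the text.

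Section 2.5.3 also leaves the post-treatment period unchanged. If its 10-day rule governed TEAEs, days 4 to 10 after the last dose would be treatment-emergent under 2.5.3 and post-treatment under 2.1.4 and 2.1.4.2. One event could then appear in both sets of tables.

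The hypoglycemia section has a further problem of its own. It takes events from one window and divides by the length of another, while citing the same section for both. The exposure rule enters every hypoglycemia rate, for completers as well as early stoppers.

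Efficacy is summarised only descriptively, and 2.4.5.2 makes TEAEs the primary focus of adverse event reporting. The window also feeds the PCSA incidences, the Kaplan-Meier curve for first severe or documented hypoglycemia, and the table of TEAEs leading to death. In an open-label trial it is better not to settle such a rule after events have been seen.

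**Working it through.** **Inputs.** IMP duration D = last dose date − first dose date + 1 (2.4.3.1). Windows ending 3 days after the last dose (2.1.4), or 10 days and 1 day after it (2.5.3). Exposure for hypoglycemia = IMP duration + 1 (2.4.5.1). 120 patients per arm (1.3). The SAP gives no discontinuation rate or event rate, so those used below are assumptions.

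**Length of each window.** A window ending k days after the last dose lasts (last + k) − first + 1 = D + k days.

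| Rule | Length | D = 182 | D = 28 |
|---|---|---|---|
| 2.1.4, all safety data | D + 3 | 185 | 31 |
| 2.5.3, adverse events | D + 10 | 192 | 38 |
| 2.5.3, hypoglycemia | D + 1 | 183 | 29 |
| 2.4.5.1, exposure as stated | D + 1 | 183 | 29 |

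The stated exposure is D + 1. If the added day merely repeats the inclusive-day correction already in 2.4.3.1, exposure is D. Neither equals the D + 3 of the section that 2.4.5.1 cites.

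**Hypoglycemia denominator.** Rates use total exposure, so the shortfall is pooled. Against D + 3 it is 2 days per patient, or 120 × 2 = 240 days per arm. On the D reading it is 120 × 3 = 360 days.

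- All treated 182 days: 120 × 185 = 22,200 days = 60.78 patient-years. With D + 1: 120 × 183 = 21,960 days = 60.12 patient-years. Shortfall 240/22,200 = 1.1%. On the D reading: 21,840 days = 59.79 patient-years, 360/22,200 = 1.6%.
- 20% stop at day 30 (assumed): 96 × 185 + 24 × 33 = 18,552 days. 240/18,552 = 1.3%; D reading 1.9%.
- 20% stop at day 7 (assumed): 96 × 185 + 24 × 10 = 18,000 days. 240/18,000 = 1.3%; D reading 2.0%.
- 50% stop at day 30 (assumed, extreme): 60 × 185 + 60 × 33 = 13,080 days. 240/13,080 = 1.8%; D reading 2.8%.

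These shortfalls apply if events are counted on D + 3, as 2.4.5.1 says. If both counts and exposure used D + 1, the mismatch would be zero.

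**Hypoglycemia numerator.** Events on days 2 and 3 after the last dose are counted under 2.1.4 and excluded under 2.5.3. This applies to completers too, because their follow-up lasts 3 days. The SAP gives no event rate from which to size it.

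**Adverse event rows.** Days 4 to 10 are 7 days per patient. Completers are followed for only 3 days, so the effect is mainly in patients who stop IMP early and remain in the study, as 1.1 allows. Patients per arm who change a given row = 120 × (share stopping early and staying) × (share of those whose first event for that row falls on days 4 to 10). All rates are assumed:

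- 5% and 2%: 120 × 0.05 × 0.02 = 0.1 patients (0.1 percentage points)
- 10% and 5%: 120 × 0.10 × 0.05 = 0.6 patients (0.5 points)
- 20% and 10%: 120 × 0.20 × 0.10 = 2.4 patients (2.0 points)

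**The case against.** The strongest reply is that the hypoglycemia exposure rule is a wrong cross-reference and not a separate error. D + 1 agrees exactly with the 1-day hypoglycemia window of 2.5.3. If events were counted on that window, numerator and denominator would match. This is true, and it may show what was intended. But 2.4.5.1 cites 2.1.4 for both, so the text as written still divides D + 3 days of events by D + 1 days of exposure.

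For adverse events, the cross-references favour 3 days: 2.4.5 points to 2.1.4, and no safety section cites 2.5.3 for the window. That is a good reason to keep 3 days, but it does not remove a paragraph that declares its own window for these analyses.

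It can also be said that reading the exposure as D is strained, since 2.4.3.1 already counts both end days. That is fair, and the D figures are best taken as an upper bound. The case of 2.4 patients combines the highest assumed rates and is a stress case.

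Finally, the effects are small. The rate error largely cancels between arms because both use the same rule. Reclassified adverse events still appear in the on-study and post-treatment tables of 2.4.5.2, and no formal test depends on them. This limits the severity of the point but leaves the contradiction in place.

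**Conclusion.** The SAP contradicts itself on the treatment-emergent window, and 2.4.5.1 does not match the section it cites. This should be fixed before database lock. It threatens the reproducibility of the safety tables more than their message.

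If hypoglycemia is counted on the 2.1.4 window, exposure as stated is short by 1.1% with full completion and by up to 1.8% if half the patients stop at day 30. It is short by at most 2.8% on the less natural D reading. If the sponsor intends the 1-day window for both counts and exposure, the rate error disappears and only the citation is wrong. For adverse events, the change per table row runs from a negligible 0.1 to 2.4 patients per arm, resting wholly on assumed stopping and event rates. The effect on PCSA incidences was not quantified.

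**What to change.** Reconcile 2.1.4, 2.1.4.2, 2.4.5.1 and 2.5.3 to one stated window per event type.

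- **Adverse events and PCSAs:** 3 days after the last dose has the most support within the SAP. It appears in 2.1.4 and 2.1.4.2, is applied by 2.4.5, and matches the 3-day follow-up in 1.1 and the concomitant-medication period in 2.1.2.
- **Hypoglycemia:** the sponsor should state the intended window and use it for both counting and exposure, written as exposure = D + k for a window ending k days after the last dose, with D as in 2.4.3.1. The existing exposure rule fits k = 1 and the 2.1.4 citation fits k = 3, so one of them must change.
- **Section 2.5.3:** delete the TEAE paragraph or align it with the chosen windows. This includes its second clause, which matters only for dosing after Visit 19, or after Day 182 when that visit date is missing.

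The cost is SAP wording and one derivation rule, with no new data. If 3 days is kept for adverse events, events on days 4 to 10 in early stoppers will appear only in the on-study and post-treatment tables.

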2.5.4 Unscheduled visits

Unscheduled visit measurements of laboratory data, vital signs, and etc. but will be used for computation of baseline, the last on-treatment value, PCSAs, and the shift summaries for safety or efficacy. They will be included in the by-visit summaries if they are re-allocated to scheduled visits.

2.5.5 Pooling of centers for statistical analyses

Center or pooling of centers is not planned and will not be included in the statistical models for efficacy analyses.

2.5.6 Statistical technical issues

N/A.

3 INTERIM ANALYSIS

No formal interim analysis is planned for this study.

4 DATABASE LOCK

The database is planned to be locked approximately 8 weeks after the last patient last visit.

5 SOFTWARE DOCUMENTATION

All summaries and statistical analyses will be generated using SAS® version 9.2 or higher.

7 LIST OF APPENDICES

Appendix A Potentially clinically significant abnormalities criteria

Appendix B Summary of statistical analyses

Appendix C Study flow chart

Appendix A Potentially clinically significant abnormalities criteria

CRITERIA for POTENTIALLY CLINICALLY SIGNIFICANT ABNORMALITIES for phase 2/3 studies (oncology excepted) (From BTD-009536 May 21, 2014)	
PCSA	Comments
Clinical Chemistry	
By distribution analysis : >3 ULN >5 ULN >10 ULN >20 ULN	Enzymes activities must be expressed in ULN, not in IU/L. Concept paper on DILI – FDA draft Guidance Oct 2007. Internal DILI WG Oct 2008. Categories are cumulative. First row is mandatory. Rows following one mentioning zero can be deleted.
By distribution analysis : >3 ULN >5 ULN >10 ULN >20 ULN	Enzymes activities must be expressed in ULN, not in IU/L. Concept paper on DILI – FDA draft Guidance Oct 2007. Internal DILI WG Oct 2008. Categories are cumulative. First row is mandatory. Rows following one mentioning zero can be deleted.
>1.5 ULN	Enzymes activities must be expressed in ULN, not in IU/L. Concept paper on DILI – FDA draft Guidance Oct 2007. Internal DILI WG Oct 2008.

CRITERIA for POTENTIALLY CLINICALLY SIGNIFICANT ABNORMALITIES
for phase 2/3 studies (oncology excepted)
(From BTD-009536 May 21, 2014)

PCSA	Comments
>1.5 ULN >2 ULN	Must be expressed in ULN, not in µmol/L or mg/L. Categories are cumulative. Concept paper on DILI – FDA draft Guidance Oct 2007. Internal DILI WG Oct 2008.
>35% Total Bilirubin and TBILI>1.5 ULN	Conjugated bilirubin dosed on a case-by-case basis.
ALT>3 ULN and TBILI>2 ULN	Concept paper on DILI – FDA draft Guidance Oct 2007. Internal DILI WG Oct 2008. To be counted within a same treatment phase, whatever the interval between measurements.
>3 ULN >10 ULN	FDA Feb 2005. Am J Cardiol April 2006. Categories are cumulative. First row is mandatory. Rows following one mentioning zero can be deleted.
<15 (end stage renal disease) ≥15 - <30 (severe decrease in GFR) ≥30 - < 60 (moderate decrease in GFR) ≥60 - <90 (mild decrease in GFR) ≥ 90 (normal GFR)	FDA draft Guidance 2010 Pharmacokinetics in patients with impaired renal function-study design, data analysis, and impact on dosing and labeling

CRITERIA for POTENTIALLY CLINICALLY SIGNIFICANT ABNORMALITIES
for phase 2/3 studies (oncology excepted)
(From BTD-009536 May 21, 2014)

PCSA	Comments
<15 (end stage renal disease)	FDA draft Guidance 2010
≥15 - <30 (severe decrease in GFR)	Pharmacokinetics in patients with impaired renal function-study design, data analysis, and impact on dosing and labeling
≥30 - < 60 (moderate decrease in GFR)	
≥60 - <90 (mild decrease in GFR)	
≥ 90 (normal GFR)	
≥150 µmol/L (Adults)	Benichou C., 1994.
≥30% change from baseline	
≥100% change from baseline	
>408 µmol/L	Harrison- Principles of internal Medicine 17 th Ed., 2008.
<120 µmol/L	
≥17 mmol/L	
<80 mmol/L	
>115 mmol/L	
≤129 mmol/L	
≥160 mmol/L	
<3 mmol/L	FDA Feb 2005.
≥5.5 mmol/L	
≥7.74 mmol/L	Threshold for therapeutic intervention.
≥4.6 mmol/L	Threshold for therapeutic intervention.

CRITERIA for POTENTIALLY CLINICALLY SIGNIFICANT ABNORMALITIES
for phase 2/3 studies (oncology excepted)
(From BTD-009536 May 21, 2014)

PCSA	Comments
≥3 ULN	
≥3 ULN	
≤3.9 mmol/L and <LLN	ADA May 2005.
≥11.1 mmol/L (unfasted); ≥7 mmol/L (fasted)	ADA Jan 2008.
>8%	
≤25 g/L	
>2 ULN or >10 mg/L (if ULN not provided)	FDA Sept 2005.
Hematology	
<3.0 Giga/L (Non-Black); <2.0 Giga/L (Black)	Increase in WBC: not relevant.
≥16.0 Giga/L	To be interpreted only if no differential count available.
>4.0 Giga/L	
<1.5 Giga/L (Non-Black); <1.0 Giga/L (Black)	International Consensus meeting on drug-induced blood cytopenias, 1991. FDA criteria.
>0.7 Giga/L	
>0.1 Giga/L	
>0.5 Giga/L or >ULN (if ULN ≥ 0.5 Giga/L)	Harrison- Principles of internal Medicine 17 th Ed., 2008.

CRITERIA for POTENTIALLY CLINICALLY SIGNIFICANT ABNORMALITIES
for phase 2/3 studies (oncology excepted)
(From BTD-009536 May 21, 2014)

PCSA	Comments
≤ 115 g/L (Male); ≤ 95 g/L (Female) ≥ 185 g/L (Male); ≥ 165 g/L (Female) Decrease from Baseline ≥ 20 g/L	Criteria based upon decrease from baseline are more relevant than based on absolute value. Other categories for decrease from baseline can be used (≥ 30 g/L, ≥ 40 g/L, ≥ 50 g/L).
≤ 0.37 v/v (Male) ; ≤ 0.32 v/v (Female) ≥ 0.55 v/v (Male) ; ≥ 0.5 v/v (Female)	
≥ 6 Tera/L	Unless specifically required for particular drug development, the analysis is redundant with that of Hb. Otherwise, consider FDA criteria.
< 100 Giga/L ≥ 700 Giga/L	International Consensus meeting on drug-induced blood cytopenias, 1991.
Urinalysis	
≤ 4.6 ≥ 8	
Vital signs	
≤ 50 bpm and decrease from baseline ≥ 20 bpm ≥ 120 bpm and increase from baseline ≥ 20 bpm	To be applied for all positions (including missing) except STANDING.
≤ 95 mmHg and decrease from baseline ≥ 20 mmHg ≥ 160 mmHg and increase from baseline ≥ 20 mmHg	To be applied for all positions (including missing) except STANDING.

CRITERIA for POTENTIALLY CLINICALLY SIGNIFICANT ABNORMALITIES
for phase 2/3 studies (oncology excepted)
(From BTD-009536 May 21, 2014)

PCSA	Comments
≤45 mmHg and decrease from baseline ≥10 mmHg ≥110 mmHg and increase from baseline ≥10 mmHg	To be applied for all positions (including missing) except STANDING.
≤-20 mmHg ≤-10 mmHg	
≥5% increase from baseline ≥5% decrease from baseline	FDA Feb 2007.

**CRITERIA for POTENTIALLY CLINICALLY SIGNIFICANT ABNORMALITIES
 for phase 2/3 studies (oncology excepted)
 (From BTD-009536 May 21, 2014)**

PCSA	Comments
ECG	Ref.: ICH E14 guidance (2005) and E14 Q&A (2012), and Cardiac Safety Research Consortium White Paper on PR and QRS (Nada et al. Am Heart J. 2013; 165(4) : 489-500)
HR	
<50 bpm <50 bpm and decrease from baseline \geq20 bpm <40 bpm <40 bpm and decrease from baseline \geq20 bpm <30 bpm <30 bpm and decrease from baseline \geq20 bpm
 
>90 bpm >90 bpm and increase from baseline \geq20bpm >100 bpm >100 bpm and increase from baseline \geq20bpm >120 bpm >120 bpm and increase from baseline \geq20 bpm

PR	
>200 ms >200 ms and increase from baseline \geq25% > 220 ms >220 ms and increase from baseline \geq25% > 240 ms > 240 ms and increase from baseline \geq25%

CRITERIA for POTENTIALLY CLINICALLY SIGNIFICANT ABNORMALITIES
for phase 2/3 studies (oncology excepted)
(From BTD-009536 May 21, 2014)

PCSA	Comments
QRS	>110 ms >110 msec and increase from baseline $\geq 25\%$ >120 ms >120 ms and increase from baseline $\geq 25\%$
QT	>500 ms
QTc	Absolute values (ms) >450 ms >480 ms >500 ms Increase from baseline Increase from baseline [30-60] ms Increase from baseline >60 ms

